SINEMET IN AMYOTROPHIC LATERAL SCLEROSIS AND PRIMARY LATERAL SCLEROSIS

Protocol Number: Sinemet-001

Sponsor: Washington University

Version 1.1, 03/13/2019

Project Title:

Carbidopa/levodopa for Spasticity in Amyotrophic Lateral Sclerosis and Primary Lateral Sclerosis Patients

Background

Amyotrophic lateral sclerosis (ALS) is a progressive neurodegenerative disease affecting motor neurons. Clinically, ALS manifests with lower motor neuron signs (weakness, atrophy, fasciculation) and upper motor neuron signs (weakness and spasticity). Primary lateral sclerosis (PLS) is similar, however it has only upper motor neuron manifestations. ALS can present initially in any body segment, with asymmetric limb weakness being the most common presentation. From initial presentation, the disease continues to progress to affect other limbs or bulbar (facial) musculature in a pattern without remissions or exacerbations. ALS eventually progresses to affect the respiratory and bulbar musculature leading to life-threatening respiratory failure and dysphagia (difficulty swallowing). The median survival time from diagnosis is 3-5 years. PLS follows a similar progression affecting various body sites, but generally progresses more slowly. Current treatments for ALS are limited, with only riluzole being shown to have effect on survival. Edaravone has been shown to slow functional deterioration in some ALS patients.

There is also a lack of symptomatic treatments for ALS and PLS patients. Spasticity in particular can become severe enough in some patients to be debilitating causing chronic pain and reducing patient's functional capacity. These patients can have limited response to medications currently indicated to treat spasticity such as baclofen and tizanidine.

Anecdotally, there is evidence levodopa, a precursor to dopamine, can improve spasticity in some ALS/PLS patients with severe spasticity. Carbidopa-levodopa (Sinemet), a combination medication that improves the efficacy of levodopa, is a mainstay of treatment of Parkinson's disease making it interesting that it might have an effect in ALS and PLS patients. In Parkinson's disease patients, carbidopa-levodopa markedly improved patients' rigidity. At the extreme spasticity that can be seen in ALS and PLS, spasticity and rigidity are difficult to distinguish.

Motivated by the success of dopaminergic drugs in treating rigidity associated with Parkinson's disease, some neurologists have used carbidopa-levodopa to attempt to improve spasticity in ALS and PLS patients. However, data on the efficacy of carbidopa/levodopa is limited. In unpublished data at this institution (Table 1) carbidopa-levodopa reduced spasticity and improved function in about half of the ALS and PLS patients that received the drug. Given the limited data and potential to improve the quality of life of these patients, the effectiveness of carbidopa-levodopa in ALS and PLS patients with severe spasticity should be studied. Our hypothesis is that administration of carbidopa-levodopa will improve spasticity in ALS and PLS patients.

Objectives

1. Determine the effect of carbidopa-levodopa on spasticity in ALS and PLS patients by a patient reported outcome measure.
2. Determine the effect of carbidopa-levodopa on objective motor function in patients with ALS and PLS.

Significance

ALS and PLS are neurodegenerative diseases of the motor tract that markedly reduce patients' function. In addition to the lack of curative therapies, there is a lack of symptomatic treatments. Spasticity is a key symptom of ALS and PLS that causes pain and limits patient function. The potential for carbidopa-levodopa to improve spasticity in these patients is intriguing. If carbidopa/levodopa is effective in reducing spasticity in these patients, they could have improvement in their functional status.

Research Plan

Design: This study is an interventional, placebo-controlled, single site, double-blind randomized crossover clinical trial. Identified participants will be randomized to receive either placebo or carbidopa-levodopa for a period of three weeks before crossing over to the other arm of the study. The two periods will be separated by a one day washout period. Below is a schematic showing examples of the randomized treatment periods. Where A represents a 3 week treatment period with carbidopa-levodopa and B represents a 3 week treatment period with placebo.

Participant 1: A->washout day->B

Participant 2: B->washout day->A

Subjective data will be collected weekly via a instruments measuring spasticity, pain, and spasm. Objective data will be collected at enrollment and at the end of each three week period via a study visit. The Columbia Suicide Severity Rating Scale (CSSR-S) will also be performed at enrollment and at the end of each three week period during study visits, as suicidal ideation is a potential serious side effect of the drug. The study team will review the responses to the CSSR-S immediately during the study visit, and if a participant answers "yes" to any of the questions, the study PI will be notified immediately. Any adverse events or side effects will be discussed at each study visit. Additionally, participants will be contacted by the study coordinator by phone one week after the first visit and one week after the participants cross over to the other treatment group to assess for any side effects.

Study Participants: Participants will be identified by chart review of patients with a diagnosis of ALS or PLS with spasticity who are currently participating or have participated in clinical research at this institution. These patients will be contacted at the phone number recorded in the electronic medical record and asked about their interest in participating in the study. A study visit will then be scheduled where consent for enrollment will be obtained.

Inclusion Criteria: Criteria for inclusion in this study include diagnosis of ALS or PLS, age greater than 18 years, and clinically significant spasticity.

Exclusion Criteria: Participants currently taking carbidopa-levodopa or with known hypersensitivity of any component of carbidopa-levodopa, narrow-angle glaucoma, current use of a non-selective monoamine oxidase inhibitor (MAOI), a history of malignant melanoma or suspicious skin lesions, depression, suicidal ideation, psychosis, myocardial infarction, ventricular arrhythmia, severe cardiopulmonary disease, uncontrolled hypertension, asthma, renal disease, hepatic disease, endocrine disease, history of peptic ulcer, or who are pregnant and/or breastfeeding will be excluded due to risk of administration of carbidopa-levodopa. Current participation in another interventional study will also exclude participants from enrolling in this study.

Randomization: The randomization of intervention sequence will be predetermined at the onset of the study and maintained by the study coordinator. At the time of consent, each participant will be assigned the randomly generated sequence of interventions.

Intervention: The study medication of carbidopa-levodopa and placebo will be prepared at the time of study initiation according to the randomization schedule. The intervention medication will be identified as drug 1-1, 1-2, 2-1, 2-2, 3-1, etc. according to the participant number and time period. The study medication and placebo will be obtained from the research pharmacy at Washington University in St. Louis. Each capsule of carbidopa-levodopa in this study will be equivalent to half of a standard carbidopa-levodopa 25/100mg tablet. Participants will take one capsule three times a day for the first week of the study period, increasing to two capsules three times a day for the remainder of the study period. Placebo capsules will be administered in the same way.

Measurement: The outcome measurements for this trial will be of subjective and objective measures of spasticity, pain, spasm, and functional capacity. The primary outcome of this study will be patient-reported symptoms on a numerical rating scale assessing spasticity severity. This scale will be administered at enrollment and weekly during the study.

Secondary outcomes measures of this study will be subjective and objective measures of pain, spasm, patient motor function, and spasticity. Participant symptoms of pain and spasm will be assessed via weekly administration of a numerical rating scale of pain and spasm. Patient strength and spasticity will be assessed on the MRC and Ashworth scale. Lower extremity function will be assessed by the Timed Up and Go (TUG) and 10 meter walk tests. These assays will be repeated twice at each study visit. Upper extremity function will be assessed by the 9 Hole Peg Test. This test will be repeated twice per arm at each visit. The Columbia Suicide Severity Rating Scale will be performed at enrollment, and repeated at each visit.

Blinding: As described above, the intervention sequence for each patient will be known only to the study coordinator. The participants and those evaluating the participants at each study visit will be blinded to the identity of the drug the participant has been taking.

Participant Schedule Summary: Participation in this study will last for 6 weeks from the initial study visit. At the initial study visit, the participant's vital signs will be taken and the participant will undergo a neurological exam. Following this, the participant will complete the outcome measures as described above. The participant will leave with three weeks of the assigned study medication or placebo. At the end of each week, the participant will complete the spasticity, pain, and spasm numerical rating scales at home. At the end of the third week, the participant will return for a research visit where the exam and outcome measures will be repeated. The participant will cross over to the other treatment arm, and the above process will be repeated. After the second three week period, the participant will come in for a final assessment. At that point the participant's role in the study will be concluded. At each visit, potential side effects will be discussed. Over the course of the study, participants will be called by phone one week after the first visit and one week after the second visit to assess for side effects

Statistical analysis: The primary outcome data will be assessed for normality. If the data is normally distributed, analysis will be performed using ANOVA to compare the baseline and two treatment groups. Further testing for differences between groups will be carried out using the Paired-samples T-test. If the data is not normal, the non-parametric Kruskal-Wallis one way analysis of variance followed by the

Mann-Whitney U test will be used. As to the secondary variables, the data from the pain and spasm numerical rating scales will be analyzed like the spasticity data described above. The time data collected by the TUG, 10 meter walk, and 9 Hole Peg Tests will be analyzed via ANOVA, with further testing between groups performed by the Paired-samples T-test. The Ashworth scale and MRC will be compared between groups using Kruskal-Wallis one way analysis of variance followed by the Mann-Whitney U test as indicated. These non-parametric tests will be used as the Ashworth and MRC data will likely not be normally distributed.

As for sample size, given the preliminary data, we expect the intervention to have a moderate to moderate-high effect. Thus with $\alpha=0.05$, power=0.07, and expected effect size of 0.7, the required sample size is 15 participants. This number is total given this is a paired analysis with the patients serving as controls for themselves.

Data Management:

Each participant will be given a coded ID number, and the spreadsheet containing the code correlating the patient's name with their study number will be kept on an encrypted, password-protected document (known only by members of the research team), which is behind the Washington University Department of Neurology firewall (accessible only by those with a department of Neurology account). Data collected during this study will be stored in RedCap.

Potential Benefits: In a case series of patients with ALS or PLS who have received carbidopa-levodopa at the Washington University School of Medicine Neuromuscle clinic, about one half have reported improvement in their symptoms of spasticity. These improvements have ranged from feeling less tightness, to improved gait and manual dexterity. Given the limitations of this data and the apparent ineffectiveness in some patients, no benefit is certain. Participants will be provided with a \$50 gift card for their time and effort. Parking validation will also be provided for study visits.

Potential Risks: The side effects most commonly associated with carbidopa-levodopa are diarrhea, orthostatic hypotension, and somnolence. Other rare adverse effects include hallucinations and dyskinesias. The dose of carbidopa-levodopa to be used in this study is commonly used in the Parkinson's disease patient population and is well tolerated. Additionally, the titration from the equivalent of one half of a 25/100mg tab to the equivalent of a full tab over a week should reduce the incidence of side effects.

Adverse Events: Participants in this study will be informed of the possible adverse effects of the medication and instructed to call the study coordinator if they begin to exhibit any of these symptoms. In particular, at each study visit and during the phone calls after the first and second study visits, the participants will be asked about symptoms of suicidal ideation, dyskinesia, and neuroleptic malignant syndrome among other possible side effects..All adverse events will be reviewed monthly by the study PI.

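### Entry does not require stable antispastic treatment: this adds a little noise to drug versus placebo and can shift comparisons with baseline (minor; cheap to improve)

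*Combined protocol and SAP*

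**What the plan says.** The protocol's Inclusion Criteria read: "Criteria for inclusion in this study include diagnosis of ALS or PLS, age greater than 18 years, and clinically significant spasticity". Under Exclusion Criteria, the only concomitant drug uses named are current carbidopa-levodopa and non-selective MAO inhibitors. The list ends with "Current participation in another interventional study will also exclude participants from enrolling in this study", which does not reach routine antispastic prescribing.

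The Background section shows that such prescribing is relevant here: "These patients can have limited response to medications currently indicated to treat spasticity such as baclofen and tizanidine". Spasticity is also the primary outcome, scored by the patient on a numerical rating scale. On its timing, the Measurement section says: "This scale will be administered at enrollment and weekly during the study".

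The Statistical analysis section then puts the enrolment score into the primary analysis: "If the data is normally distributed, analysis will be performed using ANOVA to compare the baseline and two treatment groups". Paired t-tests between conditions follow. The sample-size paragraph rests on the within-patient comparison: "This number is total given this is a paired analysis with the patients serving as controls for themselves".

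No section specifies that antispastic drugs or doses be collected as trial data. Clinic records may hold them.

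**The concern.** A patient who began baclofen or tizanidine shortly before consent, or is still raising the dose, meets every entry condition. The enrolment score is then taken before that drug has settled, and further improvement from it falls inside the six study weeks.

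The two comparisons in the plan are affected differently.

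- **Drug versus placebo.** The order of treatments is randomised, so a patient's background trend favours drug or placebo with equal chance. It widens the spread of the paired differences and leaves their expected value alone.
- **Either treatment versus baseline.** Baseline always comes first. A background improvement raises both treatment conditions against it, whichever sequence was assigned, and can look like benefit over baseline even if carbidopa-levodopa does nothing. A recent dose reduction would push the other way.

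At stake are a small loss of power in a 15-patient trial and a baseline comparison that is harder to interpret. The ANOVA with paired follow-up tests is also planned for the timed tests and, if normally distributed, the pain and spasm scales, so the baseline problem extends to those outcomes.

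**Working it through.** **Inputs from the protocol.** n = 15, alpha = 0.05, effect size 0.7 on the paired difference, three conditions (baseline, drug, placebo), two three-week periods. Power is printed as 0.07, which is read here as 0.70. Sidedness is not stated; two-sided is assumed.

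**The plan's own figure.** Exact paired t-test power (noncentral t, 14 degrees of freedom, noncentrality 0.7 × √15 = 2.71) is 0.713. With n = 14 it is 0.678, so 15 is the smallest size reaching 0.70. The stated sample size reproduces.

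**Assumptions not in the documents.** k = 2 or 4 recent starters among 15. Each improves by T = 0.35 or 0.7 per period, in units of the SD of the paired difference. Improvement is counted as positive. Each patient is randomised 50:50 to sequence. Two shapes are used: a linear trend (T by period 1, 2T by period 2) and a plateau (T by period 1, then flat).

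**Step 1, drug versus placebo.** Under the linear trend, a starter's drug-placebo difference moves by +T or −T with equal chance. The expected difference stays 0.70 and the variance rises from 1 to 1 + (k/15)T². The effective effect size is 0.7/√(1 + (k/15)T²). For k = 4 and T = 0.7 this is 0.7/√(1 + 0.267 × 0.49) = 0.7/1.063 = 0.658. Simulated power (400,000 runs):

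| Starters | T = 0.35 | T = 0.7 |
|---|---|---|
| 0 | 0.713 (exact) | 0.713 (exact) |
| 2 | 0.705 | 0.685 |
| 4 | 0.698 | 0.659 |

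Type I error stays at 0.050 to 0.051. Under the plateau both periods move equally, the trend cancels and power stays at 0.71.

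**Step 2, shift against baseline.** Averaged over sequences, a starter on a linear trend gains (T + 2T)/2 = 1.5T in either treatment condition. The mean shift is (k/15) × 1.5T under the linear trend and (k/15) × T under the plateau.

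| Starters, T | Linear shift | Plateau shift |
|---|---|---|
| 2, 0.35 | 0.07 | 0.05 |
| 2, 0.7 | 0.14 | 0.09 |
| 4, 0.35 | 0.14 | 0.09 |
| 4, 0.7 | 0.28 | 0.19 |

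With a true drug effect of 0.7 and a linear trend, the expected drug-baseline difference becomes 0.77 to 0.84 (2 starters) or 0.84 to 0.98 (4 starters).

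**Step 3, ANOVA with an inert drug and no placebo response.** The protocol says only ANOVA, so both forms were simulated (200,000 runs), with within-patient errors of SD 1/√2 so that each paired difference has SD 1.

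| Starters, T | Repeated measures, linear | Repeated measures, plateau |
|---|---|---|
| 0 | 0.049 | 0.049 |
| 2, 0.35 | 0.053 | 0.052 |
| 2, 0.7 | 0.062 | 0.056 |
| 4, 0.35 | 0.069 | 0.060 |
| 4, 0.7 | 0.121 | 0.086 |

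A one-way ANOVA that ignores pairing rejects in 0.005 to 0.019 of runs at an assumed within-patient correlation of 0.5, and in 0.001 to 0.003 at 0.7. If scores within a patient were uncorrelated, it would reject in 0.050 to 0.097.

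**Step 4, both tests together.** With an inert drug, the chance that the repeated-measures ANOVA and the drug-placebo t-test are both significant is about 0.024 with no starters and 0.023 to 0.028 across all the scenarios above.

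**The case against.** The strongest reply is that the comparison that matters is protected. The trial is a randomised, double-blind, placebo-controlled crossover. Steps 1 and 4 show an unbiased drug-placebo difference, a held type I error and no increase of note in joint false positives. A reader might infer from the missing criterion that the trial could wrongly declare carbidopa-levodopa better than placebo. The documents do not support that: an overall ANOVA result does not by itself show that drug beats placebo, and a baseline shift would move the placebo scores as well. This part of the reply stands.

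A second reply is that the ANOVA inflation depends on the form of the test. The non-parametric alternative named in the plan is a one-way method for independent groups, so an ordinary one-way ANOVA is a plausible reading. On correlated scores it stays below 0.05 in every scenario here. That also stands, although such a test has faults of its own and the baseline shift in Step 2 is present under either form.

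A third reply is that recent starters may be few. Recruitment is by chart review among patients "who are currently participating or have participated in clinical research at this institution", and the Background describes response to these drugs as sometimes limited. Neither fact ensures a settled dose, but nothing suggests that 2 to 4 of 15 would be in mid-titration. The upper end needs 4 patients improving for six weeks at a rate per period equal to the hypothesised drug effect.

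Finally, symptom-driven dose changes during the trial could move the drug-placebo difference in either direction. An entry rule does not prevent them, their rate is not given, and under a treatment-policy reading they belong to the effect. They are not counted here. The comparison with baseline is in any case already open to placebo response and progression.

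**Conclusion.** The omission is real and its importance is minor. For drug versus placebo it costs 0 to 5 points of power (0.71 to between 0.70 and 0.66 under a continuing trend) and introduces no expected bias. Its main effect is on comparisons with the enrolment score, which shift by 0.05 to 0.28 SD. A repeated-measures ANOVA of an inert drug would then reject in 0.05 to 0.12 of trials instead of 0.05. These sizes rest on assumed numbers of starters, assumed trends and an assumed form of ANOVA; at the low end they are negligible. The point is worth raising as a cheap improvement. It is not a threat to the validity of the drug-placebo test.

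**What to change.** Add one inclusion criterion: antispastic drugs and doses unchanged for a fixed interval before enrolment, with no elective change planned during the six weeks. Four weeks is offered as an example; the figure is an assumption for the investigator to confirm. State that clinically needed changes remain permitted and that patients who have them stay in the main analysis.

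As a supporting step, record antispastic drugs and doses at the three existing visits and two existing phone calls, and describe any changes by treatment and period. The entry rule removes recent starters. The record does not prevent later changes but makes them visible.

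The cost is one line in the protocol, a short medication form and one descriptive table, with no change to the sample size or the visit schedule. The downside is that recently adjusted patients must wait. That may slightly slow recruitment, because the pool is one site's current and past research participants and the disease is progressive.

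### Does the missing choice of analysis week for the weekly spasticity score leave the primary comparison undefined?

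*Combined protocol and SAP*

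**What the plan says.** The Design paragraph separates two kinds of data. For the patient-reported scales: "Subjective data will be collected weekly via a instruments measuring spasticity, pain, and spasm". For the clinic tests: "Objective data will be collected at enrollment and at the end of each three week period via a study visit". Measurement makes the spasticity numerical rating scale primary and adds: "This scale will be administered at enrollment and weekly during the study". The Participant Schedule Summary gives the timing: "At the end of each week, the participant will complete the spasticity, pain, and spasm numerical rating scales at home". It also has the participant return at the end of the third week, when the examination and the outcome measures are done again, as they were at the initial visit.

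Under Intervention, the capsules are taken as "one capsule three times a day for the first week of the study period, increasing to two capsules three times a day" for the rest of the period, so the week 1 score follows half the later capsule count.

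The Statistical analysis paragraph says, for normally distributed data, "analysis will be performed using ANOVA to compare the baseline and two treatment groups", and then "Further testing for differences between groups will be carried out using the Paired-samples T-test". Pain and spasm ratings are handled in the same way. The sample-size paragraph has an "expected effect size of 0.7, the required sample size is 15 participants", without saying which paired difference the 0.7 describes.

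**The concern.** A paired t-test needs one value per patient per treatment. The plan collects three and does not say how they become one. Week 3 alone, the mean of weeks 2 and 3, and the mean of all three weeks each fit the wording.

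Two things would be at stake. First, with 15 patients the three summaries can fall on different sides of p = 0.05, and a choice made after unblinding would add false positives. Second, a three-week mean includes the lower-dose week, so it understates the later-dose effect if week 1 carries less of it. The pain and spasm ratings share the gap.

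**Working it through.** **Inputs from the protocol.** Three weeks per period; one enrollment score plus 3 + 3 weekly scores, so 7 per patient; week 1 at half the later capsule count; alpha 0.05; effect size 0.7; n = 15 in total.

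**Inputs the protocol does not give (assumptions).** r, the correlation between weeks of the drug-placebo differences: 0.3, 0.5, 0.7, 0.9. f, the share of the later-dose effect present in week 1: 0, 0.5 or 1. Tests are two-sided.

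**1. The plan's own figure.** Paired t-test with one value per treatment: noncentrality = 0.7 × √15 = 2.71, 14 degrees of freedom, critical value 2.145, power 0.713. The smallest n with power of at least 0.70 is 15. The printed power of 0.07 would need only n = 2, so it is most likely a slip for 0.70. A one-sided test with power 0.80 also gives 15 (power 0.824). On either reading, 15 fits a paired test on a single value per patient per treatment.

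**2. Which single value the text suggests.** The ANOVA has three levels. The visits at enrollment, end of period 1 and end of period 2 supply exactly one value for each, on the same timing as the clinic tests. The end-of-period value follows two weeks at the later dose, so under this reading the lower-dose week does not enter.

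**3. Dilution if all three weeks were averaged.** Share of the later-dose effect recovered = (2 + f)/3: 67% for f = 0, 83% for f = 0.5, 100% for f = 1.

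**4. Power at n = 15 if 0.7 is the effect in a single later-dose week.** Standardised effect = 0.7/√((1 + r)/2) for weeks 2-3, and 0.7 × [(2 + f)/3]/√((1 + 2r)/3) for weeks 1-3.

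| Summary | r = 0.5 | r = 0.7 | r = 0.9 |
|---|---|---|---|
| Week 3 | 0.71 | 0.71 | 0.71 |
| Weeks 2-3 | 0.83 | 0.78 | 0.74 |
| Weeks 1-3, f = 0 | 0.54 | 0.47 | 0.41 |
| Weeks 1-3, f = 0.5 | 0.73 | 0.65 | 0.59 |
| Weeks 1-3, f = 1 | 0.87 | 0.81 | 0.74 |

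If 0.7 is instead defined on whichever summary is used, power is 0.71 for all of them.

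**5. Disagreement and type I error, by simulation (n = 15).** Each score is a patient effect, plus a patient-by-condition effect with variance r, plus weekly error with variance 1 − r. Disagreement means that at least one but not all of the summaries compared reach p < 0.05, with a true effect of 0.7 per later-dose week. Best-of-three means that any of the three paired t-tests rejects when drug and placebo do not differ.

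| Quantity | r = 0.3 | 0.5 | 0.7 | 0.9 |
|---|---|---|---|---|
| Disagreement, all three, f = 0.5 | 0.25 | 0.23 | 0.20 | 0.18 |
| Disagreement, all three, f = 1 | 0.26 | 0.22 | 0.16 | 0.09 |
| Disagreement, week 3 against weeks 2-3 only | 0.20 | 0.16 | 0.12 | 0.07 |
| Best-of-three error, t-tests alone | 0.097 | 0.089 | 0.079 | 0.066 |
| Best-of-three error, ANOVA first, equal means | 0.040 | 0.040 | 0.037 | 0.032 |
| Best-of-three error, ANOVA first, both treatments shifted 0.5 SD from baseline | 0.069 | 0.064 | 0.057 | 0.050 |
| Best-of-three error, ANOVA first, both treatments shifted 1 SD from baseline | 0.096 | 0.085 | 0.077 | 0.064 |

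Week 3 fixed in advance, with ANOVA first and equal means, gives 0.024 to 0.025.

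The third row compares two summaries that both leave out week 1. At r = 0.3 it accounts for 0.20/0.25, about 80%, of the three-way disagreement at f = 0.5; at r = 0.9 for 0.07/0.18, about 40%. At the lower correlations, then, most of the disagreement is ordinary sampling noise between two sound summaries and has nothing to do with the half-dose week.

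**The case for a change.** The strongest case for a change is that the end-of-period visit sentence sets a schedule and does not define an endpoint. If only week 3 counted, the week 1 and week 2 scores of the primary scale would have no stated use. It is also unclear whether week 3 yields a home score, a visit score or both. Naming the value would take a sentence and no new data. The ANOVA step does not fully protect either: if both treatments shift from baseline by 1 SD, the best-of-three error returns to 0.064 to 0.096.

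The gap in wording stands, and so does the arithmetic. What does not stand is that the plan leads to a wrong result. No stated rule tells the analyst to pool week 1 or to try several summaries, and nothing says the choice would wait until after unblinding. The inflated error rates describe that behaviour and not the plan. Leaving out week 1 is itself a choice of estimand on which statisticians may differ, since the hypothesis concerns giving the drug and is not limited to the later dose. The simulations cover only the normal-data branch and say nothing about the Kruskal-Wallis and Mann-Whitney branch.

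**Conclusion.** The plan does not name the week, but this is missing detail that an analyst would fill sensibly. The three-level comparison, the paired test and the end-of-period visits favour one week 3 value per treatment. That value follows the later dose and has power 0.71 at n = 15 for the stated effect of 0.7. The mean of weeks 2 and 3 would also be sound, with power 0.74 to 0.83 for r from 0.9 down to 0.5 if 0.7 applies to each later-dose week.

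Harm needs a further step that the plan does not call for: choosing among summaries after unblinding (error up to 0.097 without the ANOVA step, 0.032 to 0.040 with it and equal means), or averaging in week 1 when it carries little effect (67% of the later-dose effect at worst, taking f between 0 and 1). The dilution and power figures rest on assumed values of r and f, and the error rates on assumed r and shift. Settling the value and its source in the analysis program before unblinding, and using it for pain and spasm too, is normal practice under the existing text. No change to the plan follows.

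### The study coordinator, the only person stated to know the treatment sequence, also makes and takes the between-visit side-effect calls, so that part of the safety record is collected unblinded

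*Combined protocol and SAP*

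**What the plan says.** The Design paragraph describes a "single site, double-blind randomized crossover clinical trial". The Randomization paragraph says the sequence is "predetermined at the onset of the study and maintained by the study coordinator", and the Blinding paragraph adds that "the intervention sequence for each patient will be known only to the study coordinator". Blinding is then promised to two groups: the participants, and the evaluators, in that "those evaluating the participants at each study visit will be blinded to the identity of the drug".

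On side effects between visits, the Design paragraph says "participants will be contacted by the study coordinator by phone one week after the first visit" and again "one week after the participants cross over to the other treatment group to assess for any side effects". The Participant Schedule Summary and the Adverse Events section mention the same calls without naming the caller. The Adverse Events section tells participants to phone the coordinator if symptoms begin. It lists suicidal ideation, dyskinesia and neuroleptic malignant syndrome among the topics of the scheduled calls and visits, and has the principal investigator review all adverse events monthly.

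The Intervention paragraph says the study drug and placebo "will be prepared at the time of study initiation according to the randomization schedule", come from the research pharmacy, and carry labels showing only participant number and period (1-1, 1-2 and so on). It does not say who prepares or labels them.

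**The concern.** The person who asks about symptoms between visits, and takes reports of them, knows which treatment the participant is on. Such knowledge can affect how a question is put, how far an answer is probed and what is written down. The symptoms at issue, such as somnolence and hallucinations, depend largely on what is asked and reported. The monthly review by the investigator does not correct this, because it works from reports already collected.

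The schedule adds weight. Each period has one call, at about one week, and the number of capsules doubles after the first week. From then until the end-of-period visit, the only side-effect route described is a participant's own call to the coordinator.

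A lesser risk is that an unblinded caller gives a cue to the participant, whose self-rating of spasticity is the primary outcome. In a two-treatment crossover, a cue in one period also points to the treatment in the other.

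**Working it through.** The plan gives no figure to reproduce. The check is a comparison of roles, followed by a count of contacts.

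**Roles, side by side**

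| Task | Person named | Where |
|---|---|---|
| Maintains the sequence | Coordinator | Randomization |
| Knows each participant's sequence | Coordinator only | Blinding |
| Makes the scheduled side-effect calls | Coordinator | Design |
| Receives symptom calls from participants | Coordinator | Adverse Events |
| Discusses side effects at visits | Nobody named | Design; Participant Schedule Summary; Adverse Events |
| Evaluates participants at visits | Blinded evaluators | Blinding |

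The first four rows name the same person, and no section provides a blinded caller. The two sections that mention the calls without naming a caller do not contradict the Design paragraph.

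**Count of scheduled on-treatment side-effect contacts**

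Inputs: n = 15 participants (sample-size paragraph); c = 2 calls per participant (Design); v = 2 on-treatment visits per participant, one at the end of each period (Participant Schedule Summary). The enrollment visit is left out because no study drug has yet been taken. All 15 are assumed to complete both periods.

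- Total: n × (c + v) = 15 × (2 + 2) = 60.
- Minimum with the coordinator, if blinded evaluators hold the visit discussions: n × c = 15 × 2 = 30, and 30/60 = 50%.
- Maximum, if the coordinator also holds the visit discussions: 60/60 = 100%.
- Scheduled contacts between visits only: 30/30 = 100% with the coordinator.

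Let m be the number of calls begun by participants. The documents give no value for it. Under the minimum case the share becomes (30 + m)/(60 + m), which is 50% at m = 0 and rises with every such call.

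These are counts of exposure. Nothing in the documents allows the size of any resulting bias to be estimated.

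**The case against.** The strongest reply is that no promise is broken. The Blinding paragraph defines who is blinded, namely participants and visit evaluators, and the coordinator is in neither group by virtue of the calls. That stands: this is a gap in the scope of blinding, not a contradiction in the text.

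The consequences are also bounded. No between-treatment test of adverse events is planned, so no test result is at stake. Suicidal ideation is also assessed with a rating scale at each visit, and side effects in general are asked about again there. These are real mitigations. They do not blind what is gathered between visits, and the rating scale covers only one of the listed symptoms.

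Someone must hold the list, and in a small single-site study the coordinator is a natural choice. That is fair, but it need not be the person assigned all the between-visit symptom calls, and a pharmacy is already involved.

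A reader might go further and infer that participants are unblinded, or that the primary outcome is biased. The documents do not support either. The weekly ratings are completed by the participant at home, no section has the coordinator collect or score efficacy measures, and nothing shows that a cue would be given.

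A reader might also infer that all adverse event collection is unblinded. That would require the coordinator to lead the visit discussions, which the documents neither say nor rule out.

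**Conclusion.** The concern holds for the record of adverse events between visits. Both routes, scheduled and participant-initiated, go to the one person stated to know the sequence. The overlap of roles is certain on the text. The unblinded share of scheduled on-treatment contacts is 50% to 100% (30 to 60 of 60), and the width of that range comes entirely from the plan not saying who discusses side effects at visits. The count assumes 15 participants who complete both periods.

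The effect on the safety record cannot be quantified, and any effect on participant blinding or the primary outcome remains a possibility only. The change is worth making before enrollment because it is cheap, and because reports gathered by an unblinded person cannot be made blinded afterwards.

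**What to change.** Amend the Randomization and Blinding paragraphs as follows.

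1. The sequence list, the code-break and the labelling of capsules are held by someone with no participant contact. The research pharmacy is the obvious candidate, since it already supplies the capsules.
2. The coordinator works only from the participant-period labels and keeps both the scheduled and the incoming calls.
3. The Blinding paragraph states that whoever phones participants or takes their calls is blinded.

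The cost is the rewording of two paragraphs and the transfer of the list, with no new staff if the pharmacy can take this on. Its capacity must be confirmed, and the list holder must be reachable for emergency unblinding. If the coordinator currently labels the capsules, that work must move too: 2 × 15 = 30 participant-period supplies. A list the coordinator has already seen must be regenerated.
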